#### 5.4 Data Collection

- The use feasibility data will be collected by a daily event monitoring log designed specifically for this study which will be recorded manually by subjects everyday throughout the study period.
- Data collected by the iThermonitor is automatically uploaded to a paired receiver within a range of five meters for cloud storage. These data will be downloaded on a weekly basis and stored in the Partners Healthcare network of computer files available to only the IRB approved study staff at the Partners Connected Health Innovation. Partners Connected Health Innovation is an established leader in the creation and implementation of effective healthcare delivery strategies supported by patient-centric technology. At PCHI, we leverage information technology – mobile phones and apps, remote monitoring tools, personal health trackers, sensors, computers and networked devices – to help providers and patients manage chronic conditions, maintain health and wellness, and improve adherence, engagement and clinical outcomes.
- We will collect information about the participant’s type of cancer, stage of disease and treatment regimens from a review of the electronic medical records.
- Enrollment, usability and satisfaction data will be collected by questionnaires designed specifically for this study.

Outcome data will be stored in computer network files that are accessible only to IRB approved study staff. Outcome data will be linked to each subject by a unique number, which will not have any identifying information. All data collected will be analyzed at the end of the study period.

A summary of data points to be assessed in this study is summarized in the table below:

Assessments	At entry	During the study	Close out (+/- 5days)
Enrollment questionnaires	X		
Temperature measurements via device	X	X	
Daily event monitoring log		X	X

Number of out-of-range temperature episodes detected		X	
Usability and satisfaction questionnaires and other closeout surveys			X
GAD-7	X		X

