### 5.5 Risks and Privacy Concerns:

We do not foresee any significant risks for subjects/caregivers:

- Participants will continue to receive usual treatments including having their temperature monitored by their clinical team and caregivers according to standard care protocols.
- Participants are free to leave the study at any point without restriction.
- While we do not expect the iThermonitor to fail, the risk involved revolves around failure to appropriately notify subject/caregiver of a true fever episode or the generation of a false out-of-range temperature alert. Therefore, we will emphasize that subjects/caregivers should continue to monitor their temperature as recommended by their care providers. In the event of an out-of-range temperature alert, we will encourage subjects/caregivers to confirm the out-of-range temperature with their personal thermometers before notifying their care providers.
- Although subjects/caregivers are asked to complete questionnaires at the start and at the end of the study they will be instructed that they can choose not to answer any question(s) they do not wish to answer.
- The study team members responsible for completing chart reviews to gather the required information will be CITI certified and well-versed in HIPAA requirements. These team members will be trained and familiarized with the process of obtaining the required data points and will minimize viewing of any non-essential information.

Data security and privacy will be maintained through:

- Separation of participant names from all study data will be done through the use of unique identifiers. Only Study ID numbers will be used on the iThermonitor Application.
- The record review will be done by IRB approved study staff and will be focused only at collecting pre-specified information namely, temperature data while on hospitalization, type and stage of cancer and treatment regimens.
- Any information transferred via the internet will be done using 128 bit SSL encryption.
- Virus and password protected facilities within the Partners Healthcare network of computers will be provided for the research team.
- To safeguard confidentiality, access to all collected data will be limited to only the IRB approved study staff. Study subjects will be referred to by a unique study number and not by name.
- All communications via telephone or other media with subjects/caregivers will be stored in their study file.

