### 6.1 Primary and secondary endpoints

6.1a Primary outcome measurement: use feasibility of the iThermonitor will be assessed by ability of the device to successfully capture, transmit and display the patient's body temperature data on the study iPad mini. To limit recall bias, subjects will be required to log (Appendix 5) the ability to view the temperature data on the iPad mini once a day for the entire duration of the study. The device will be deemed a feasible continuous temperature monitoring tool if at least 80% of study subjects are able to successfully use the iThermonitor to monitor their body temperature. A subject must be able to view temperature data on the provided iPad mini at least 80% of the time in the study to be considered successful. "Time in the study" here is defined as the number of days the subject spends in the study which is expected to be two weeks.

6.1b Secondary outcomes: secondary outcomes which will be assessed at the end of the study include:

- i. Usability, acceptability and satisfaction with the iThermonitor. This will be assessed by questionnaires specifically designed for this study. We will be assessing ease of use, acceptability, connection and use problems like the device falling off the skin, usefulness of out-of-range temperature alerts and adverse reactions. We will also assess to see if the device helps to build caregiver self-efficacy skills in caring for the patient.
- ii. Caregiver engagement with the iThermonitor. This will be assessed by time to first measurement and upload from the time of discharge and also by the frequency of logins to the iThermonitor app.
- iii. Caregiver anxiety will be assessed using the GAD-7 questionnaire.

6.2 Sample size and statistical power or precision associated with the sample size: The length of time required to accrue an adequate number of subjects to the study should be indicated.

We will be able to estimate a feasibility success rate of 80% to within a 95% confidence interval of +/- 16% with a sample size of 25 evaluable patients. This is in keeping with a

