### 6.7 Analysis plan

Data collected will be verified before analysis, which will be done with Data Analysis and Statistical Software: STATA, version 13 with an alpha of 0.05 set a priori. All participants will be followed up for two weeks and we will summarize their baseline demographic and technology use characteristics.

To address the primary aim, the feasibility success rate will be calculated as the number of evaluable patients who meet the criteria for 'success' (per section 6.1) divided by the total number of evaluable patients. A 95% confidence interval will be calculated on this proportion. If the upper limit of the 95% confidence interval is less than 80%, then we will consider the iThermonitor not to be a feasible clinical decision support tool.

Descriptive analyses will be performed on all baseline data. Endpoints for all study outcomes are defined in section 6.1 above. All continuous variables will be computed as means with standard deviations, median and ranges while categorical variables will be computed as frequency distributions and percentages. The binomial test of proportion will be used to our dichotomous outcome of successfully using the iThermonitor. Paired t-test will be used to

analyze pre- and post- GAD-7 scores measured as a continuous variable. All other outcome variables will be summarized with descriptive statistics.

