#### 6.8 Handling of missing data in the analysis

We have adopted simple data collection techniques to limit missing data for this trial. Since this is largely exploratory work with descriptive statistics, a complete case analysis approach will be adopted for this study. .

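### Dyads that stop early without being hospitalised are scored on a shortened period or may be left out, and blank log days have no rule, so the primary success rate can be too high and the 80% verdict can change

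*Combined protocol and SAP*

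**What the plan says.** All references are to the combined protocol and SAP.

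- **Subject level (6.1a; the same definition is in 2.1).** Success means viewing temperature data on the study iPad mini for at least 80% of the time in the study, which "here is defined as the number of days the subject spends in the study which is expected to be two weeks".
- **Study level (6.1a, 6.7).** The device is feasible if at least 80% of subjects succeed. The rate is successes "divided by the total number of evaluable patients". The device is judged not feasible on this condition: "If the upper limit of the 95% confidence interval is less than 80" per cent.
- **Follow-up (6.7).** "All participants will be followed up for two weeks".
- **Missing data (6.8).** "a complete case analysis approach will be adopted for this study". The text does not say whether a case is a dyad or a log day.
- **Leaving (5.5).** "Participants are free to leave the study at any point without restriction".
- **Removal (5.63, 6.6).** The one stated rule is for hospitalised subjects. Those with under 7 days of use are dropped and replaced, and those with at least half the data are kept.
- **Data source (5.4, Appendix 5.2).** The endpoint comes from a 14-row Yes/No log "which will be recorded manually by subjects everyday throughout the study period". Device data are also uploaded: "These data will be downloaded on a weekly basis".

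**The concern.** The study asks whether families can use the device at home for two weeks. A family that gives up early is direct evidence on that question. Under the plan it is judged only on the days before it left, so it fails only if viewing was already poor in those days, or else it may drop out of the analysis. Either way the plan is lenient towards dyads that quit, and with 25 dyads each one moves the rate by 4 points. The feasibility verdict in 6.1 could then depend on how leavers are handled.

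Blank log days raise the same problem on a smaller scale. The plan does not say whether a blank means not viewed, is left out of the day count, or makes the dyad incomplete.

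**Working it through.** **The plan's own figure.** For 80% and n = 25, the half-width is 1.96 × √(0.8 × 0.2/25) = 0.157, which agrees with the ±16% in 6.2. The precision statement is not in dispute.

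**One leaver.** The viewed days needed for 80% are 4 of 5, 6 of 7 and 12 of 14.
- Stops on day 5 with 4 viewed: 4/5 = 80% (success) on days in study; 4/14 = 29% (failure) on 14 days.
- Leaves after day 7 with 6 viewed: 6/7 = 85.7% (success) against 6/14 = 42.9% (failure).

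**Study level.** Assume 25 dyads, F completers who fail, L leavers with fewer than 12 viewed days, no hospitalisation and no replacement. Let s be the number of leavers who reach 80% of their own days.
- Left out: (25 − F − L)/(25 − L)
- Shortened time: (25 − F − L + s)/25
- 14 days: (25 − F − L)/25

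With every leaver at 4 of 5 days (s = L):

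| F | L | Left out | Shortened time | 14 days |
|---|---|---|---|---|
| 4 | 1 | 20/24 = 83.3% | 21/25 = 84.0% | 20/25 = 80.0% |
| 4 | 2 | 19/23 = 82.6% | 21/25 = 84.0% | 19/25 = 76.0% |
| 4 | 3 | 18/22 = 81.8% | 21/25 = 84.0% | 18/25 = 72.0% |
| 3 | 3 | 19/22 = 86.4% | 22/25 = 88.0% | 19/25 = 76.0% |

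Leaving dyads out meets 80% when L ≤ 25 − 5F. The 14-day score misses 80% when L ≥ 6 − F. The two verdicts therefore differ for L = 2 to 5 when F = 4, for L = 3 to 10 when F = 3, and for L = 4 to 15 when F = 2. One leaver with F = 4 does not split them.

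**How often a leaver scores as a success on its own days.** Assume leaving days uniform on 1 to 11 and viewed days binomial. The chance is 10%, 23%, 60% and 93% for daily viewing rates of 45%, 60%, 80% and 95%. With F = 4 and L = 3, shortened time reaches 80% once s ≥ 2, because (18 + 2)/25 = 80%. If leavers are independent, that chance is 3q²(1 − q) + q³:
- q = 0.597 (80% viewing): 64%.
- q = 0.227 (60% viewing): 13%.

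If all three viewed only 3 of 5 days, s = 0 and shortened time gives 72.0%, while leaving them out still gives 81.8%.

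**The 6.7 rule, exact (Clopper–Pearson) limits.** The upper limits for 18/22, 21/25 and 18/25 are 94.8%, 95.5% and 87.9%, so the rule is not triggered. It changes near its boundary: 15/25 has an upper limit of 78.9% (not feasible), but leaving out one failing leaver gives 15/24 with 81.2% (not ruled out).

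**Blank days.** A log with 9 Yes, 2 No and 3 blank scores 9/11 = 82% (success) if blanks are left out and 9/14 = 64% (failure) if they count as not viewed. On the strictest reading of 6.8, where a dyad needs all 14 entries, blanks independent across days at rate b remove 1 − (1 − b)¹⁴ of dyads: 25% at b = 2% and 51% at b = 5%. The latter leaves about 12 of 25, with a half-width of 1.96 × √(0.16/12) = 22.6 points. If blanks cluster within families (beta-binomial, assumed intra-dyad correlation 1/3), the losses fall to about 9% and 21%.

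**The case against.** The strongest reply is that the plan does state a denominator. Sections 2.1 and 6.1 both use days actually spent in the study, and 6.6 lists only one class of removal. Read together, a leaver is evaluable and scored on its own days. The follow-up sentence in 6.7 describes intended follow-up and is not a rival denominator. This stands. A reader might infer that the text offers 14 days as a competing reading, but it does not: 14 days is only the expected duration, and the 14-day score here is the proposed remedy. Nor is it certain that complete case analysis removes a leaver whose log is full up to the day it left. It may do so.

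Where leavers viewed 4 of 5 days, the two routes the text supports agree on the verdict in every row of the table. The gap is between both of them and a score over the planned period. For families who leave because viewing was poor, shortened time often fails them anyway.

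Replacement is a fair point too. The plan replaces the one class it removes, and if leavers were replaced, 18/22 would not occur as such. That restores the count of 25 but does not bring the leavers back. If replacements succeeded at the completers' rate, the expected result would still be 81.8%.

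A reader might also infer that the trial's result will be biased upwards by a known amount. The documents do not support that. They give no withdrawal rate, and the day-2 call (5.63) and payment on completion (5.68) may keep leavers few.

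Finally, a leaver with 6 of 7 viewed days would fail under the remedy while a retained hospitalised dyad with the same log succeeds. The difference is defensible. The protocol itself ends device use on admission, whereas a leaver's remaining home days were available for use.

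**Conclusion.** The point holds as a weakness in the endpoint rule and should be fixed. The days-in-study rule, and complete case analysis if it removes leavers, both favour feasibility when families quit. Neither treats quitting as a failure to use the device for 14 days. The effect on the 6.1 criterion can be decisive at modest numbers: with four failing completers and three leavers, 81.8% or 84.0% against 72.0%. That illustration assumes 25 dyads, no replacement and, for the 84.0%, leavers who each viewed 4 of 5 days.

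An upward effect is plausible but not proven, and its size is unknown. The 6.7 upper-limit rule is largely insensitive and moves only near 15 of 25. The silence on blank days is a clear gap that can decide a dyad's status, but the loss of dyads it could cause depends on a strict reading of 6.8 and on how blanks cluster. Confidence is high on what the text says and leaves unsaid, and low on how much it will matter in this trial.

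**What to change.** 1. **6.1 and 6.8.** For dyads not hospitalised, score the primary endpoint on the 14 scheduled days (at least 12 viewed), in place of complete case. Days after withdrawal, and days on which the device was never set up, count as not viewed. A dyad that leaves after 12 viewed days is still a success. Keep the days-in-study version as a sensitivity analysis.
2. **Blank log days.** State one rule, for example not viewed in the primary analysis. Report two sensitivity analyses: blanks left out, and blanks counted as viewed where the device upload holds data for that day. The latter is generous, since an upload shows that data arrived, not that anyone looked.
3. **6.7.** Beside the evaluable-set rate, report successes over all enrolled dyads, with the number of and reasons for removals and replacements.
4. **5.63 and 6.6, for analysis only.** Clarify whether the existing 7-day cut counts calendar days at home or days worn. Keep hospitalised dyads retained under that rule scored on their home days. When device use stops is not affected.

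**Cost.** Wording in these sections and a few extra result lines, from data already collected. The reported rate may be lower. Withdrawals unrelated to the device, or missing paperwork, can count as failures: three blanks fail a dyad that viewed every day (11/14 = 79%). With independent blanks that would affect 3% of such dyads at a 5% blank rate and 16% at 10%. The reasons and the sensitivity results should therefore be shown with the primary rate.

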### 5.61 Enrollment visit:

This will take place during the clinic visit for chemotherapy or on the day before discharge for hospitalized patients.

- Enrollment into the study by signing the informed consent form. This will be done before performing any study procedures.
- Rescreening to confirm eligibility as described above. A screening checklist will be provided to guide the RA.
- Complete all enrollment surveys. Caregivers will be required to complete the GAD-7
- The research assistant will explain and demonstrate how to use the iThermonitor and also leave subjects with user manuals. (Appendices 1.4.)
- Subjects who wish to use their own smartphones, in addition to the provided study iPad minis, will be instructed to download the iThermonitor's app on the app store.
- Finally, study staff will emphasize that the iThermonitor is not a replacement for usual temperature monitoring protocols and will instruct participants to continue to receive medical care from their physicians as usual.

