#### 5.64 Close out visit:

- This visit will occur 2 weeks post-chemotherapy. If possible, subjects will schedule their final study visit at the enrollment visit. Study staff will also send an appointment reminder letter in the mail 3 days prior to the scheduled visit. They will also receive a reminder phone call to confirm the appointment a day before the final study visit. If participants would like, they can complete close-out surveys online via RedCap and return study devices during their next doctor visit or via a provided pre-paid FedEx envelope.

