#### 5.68 Remuneration

Each patient-caregiver dyad will receive a Partners-issued check of \$100 after completing the final study visit and returning the study iPad mini. The check will be mailed at the end of the study. No additional remuneration or reimbursement will be provided.

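### Questionnaire-based secondary outcomes are scheduled only at close-out, with nothing for dyads that withdraw, so acceptability may be overstated

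*Combined protocol and SAP*

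**What the plan says.** Section 6.1b introduces its list with "secondary outcomes which will be assessed at the end of the study include". The list covers usability, acceptability and satisfaction (by questionnaire), caregiver engagement (by uploads and app logins) and caregiver anxiety (by GAD-7).

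The assessment table in 5.4 marks "Usability and satisfaction questionnaires and other closeout surveys" in the close-out column alone, with a window of 5 days either side. The GAD-7 is marked at entry and at close-out. The baseline score comes from the enrollment visit in 5.61: "Caregivers will be required to complete the GAD-7". For close-out, 5.64 states: "This visit will occur 2 weeks post-chemotherapy". It also allows the surveys to be completed online through REDCap.

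On leaving, 5.5 says: "Participants are free to leave the study at any point without restriction". Sections 5.63 and 6.6 set a rule for children admitted to hospital. I found none for families that withdraw by choice. Under 5.68 the $100 is paid "after completing the final study visit and returning the study iPad mini". Section 6.7 uses a paired t-test to "analyze pre- and post- GAD-7 scores measured as a continuous variable", and under 6.8 "a complete case analysis approach will be adopted for this study".

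**The concern.** The close-out questionnaire (Appendix 4.1) asks whether the device stayed on, what problems arose, whether alerts were useful and whether the family would go on using it. Difficulty on any of these is a plausible reason to withdraw. The protocol itself foresees skin reactions (5.7) and false alerts (5.5). Whether a dyad answers may therefore depend on what it would have answered.

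With one post-baseline time point, no assessment at withdrawal and complete-case analysis, a dyad that withdraws early is not scheduled to contribute a usability rating, a satisfaction rating or a second GAD-7. The ratings would then lean towards families that tolerated the device. The paired GAD-7 comparison would omit any change in anxiety among families that gave up. In a feasibility study, acceptability is one of the results on which a next step would rest.

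The point is limited to voluntary withdrawal and the questionnaire-based outcomes. It does not touch the primary success rate or the rule for hospital admission.

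**Working it through.** **1. Timing.** If close-out falls on day 14, the window in the 5.4 table opens at about day 14 − 5 = 9. A dyad that withdraws on day 4 does so before any scheduled post-use questionnaire.

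**2. The plan's own figure.** Section 6.2 gives ±16% for an 80% rate with 25 evaluable patients. The Wald half-width is 1.96 × √(0.8 × 0.2 / 25) = 0.157, which reproduces it. That figure belongs to the primary outcome; none is given for the secondary outcomes. With 20 answering, the half-width is 1.96 × √(0.16 / 20) = 0.175, less than 2 points wider. The issue is therefore selection more than precision.

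**3. Range for a yes/no item.** Let N = 25 be enrolled, m not answer, r = N − m answer, and x of those be favourable. The reported value is x/r. For all N it lies between x/N (every non-answerer unfavourable) and (x + m)/N (every one favourable). The documents give no withdrawal rate, so m and x are assumptions.

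| m | r | x | Reported x/r | Low x/25 | High (x+m)/25 |
|---|---|---|---|---|---|
| 2 | 23 | 21 | 91.3% | 84% | 92% |
| 4 | 21 | 19 | 90.5% | 76% | 92% |
| 5 | 20 | 16 | 80.0% | 64% | 84% |

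The last row takes m = 20% × 25 = 5 from the inevaluable estimate in 6.6 (below 20%). That estimate accompanies the hospitalisation rule and is not a forecast of voluntary withdrawal. The range is lopsided when the reported figure is high: with m = 4 the true value could be 14.5 points lower (90.5 − 76) but only 1.5 points higher (92 − 90.5).

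**4. GAD-7.** The mean change among answerers differs from that among all 25 by (m/25) × (answerers' mean − non-answerers' mean). With m = 4 the factor is 4/25 = 0.16. As an illustration with assumed values, suppose 21 answerers average −1 and 4 non-answerers average +4. The plan would report −1.0, while the mean over all 25 is (21 × (−1) + 4 × 4)/25 = −0.2. The direction of that difference is itself assumed. The standardised change detectable with 80% power at two-sided 0.05 moves from 0.58 SD (n = 25) to 0.64 SD (n = 21) or 0.66 SD (n = 20).

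**5. Recall period.** The GAD-7 in Appendix 4.2 asks about the preceding two weeks. Completed on day 4, it would cover about 4 days of device use and 14 − 4 = 10 days before it, overlapping the baseline period. Such a score is not comparable with one taken at day 14.

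**The case against.** A reader might infer that dyads that stop never answer, and that the secondary results as a whole describe only those who stayed. The documents do not support either reading.

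- Nothing in the available text bars a leaver from close-out; the plan is silent. Section 6.7 says that all participants are followed for two weeks, although it gives no procedure for leavers. Consent pages are not among the available text, so a withdrawal procedure stated there cannot be ruled out.
- Stopping the device is not the same as leaving the study. A family that removes the patch without withdrawing keeps its scheduled close-out, the reminder letter and call, the REDCap option and the payment. Payment depends on the final visit and return of the iPad mini, not on device use, so for these families it favours a response.
- Engagement comes from uploads and logins. The daily log (Appendix 5.2) records wear and viewing day by day. Adverse events are documented separately under 5.71. A difficult experience is not wholly invisible.
- The numbers of leavers are assumed, and over two weeks they may be few. The satisfaction items use four-point scales with no cut-off, so the plan does not itself specify a percentage satisfied.
- These are secondary, mostly descriptive outcomes of a 25-dyad pilot, and the feasibility decision in 6.7 uses only the primary success rate.

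All of this stands, and it narrows the point. It does not supply an assessment, or a record of the reason, for a dyad that formally withdraws, and complete-case analysis leaves that gap out of sight.

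**Conclusion.** The point holds in limited form. The usability and satisfaction questionnaires and the post-use GAD-7 have a single scheduled post-baseline time point, nothing is provided for voluntary withdrawal, and complete cases are analysed. These results may therefore over-represent completers and overstate acceptability.

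The actual bias cannot be computed from the documents. Assuming 2 to 4 non-answering dyads of 25, a reported 90–91% satisfied is compatible with 76% to 92% of those enrolled. With no voluntary withdrawals and full response, there is no effect. The direction is plausible rather than shown. This is a cheap improvement to the secondary outcomes, not a threat to the primary endpoint.

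**What to change.** In 5.64, add that a dyad that withdraws voluntarily is offered the existing REDCap usability and satisfaction survey at the time of withdrawal, with a question on the reason for stopping. Add that the caregiver is invited to complete the GAD-7 at the scheduled close-out date rather than at withdrawal, because of its two-week recall. All of this stays voluntary.

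In 6.7 and 6.8, report the key satisfaction and acceptability results with the number enrolled as well as the number answering. For items that are dichotomised, state the cut-off in advance and give the range obtained by counting non-answerers as all unfavourable and then all favourable. Children dropped at hospital admission have their own rule in 6.6 and should be shown separately.

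The cost is a few sentences, a few extra emails and possibly a less favourable reported figure. The REDCap form and emailed link are already part of the plan.
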